7.4 Reporting Procedures

AE Reporting and Follow-up

During the post-intervention and follow-up assessments, the Research Coordinator will inquire about AEs and complete a participant event form (PEF) if an AE is reported. Likewise, MABT Interventionists will complete a PEF form if an AE is reported during check-in's prompted in the intervention protocol. PEF forms will be submitted to the project manager weekly, and all adverse events, with the exception of clinically insignificant events and minor common illnesses and injuries (e.g., cold/flu, scrapes, upset stomach, low-grade headaches) will be documented on an AE Log and will be reported every 2 weeks to the contact PI, who provides the grading and attribution evaluation. AEs will be summarized and discussed monthly amongst the core research team. AE summary reports will be provided quarterly to the independent monitor (IM), and to the NCCIH at the time of the annual progress report. Reports will provide information on cumulative incidents and if in total the events suggest that subjects or others are at greater risk, investigators and the IM will address whether or not the consent form needs to be changed. In the annual AE summary, the Independent Monitor Report will state that he has reviewed all AE reports. If an AE/SAE meets the criteria of unanticipated problem for the UW IRB, it will be reported within 10 business days. Breach in confidentiality will be reported to the IRB within 24 hours.

SAE Reporting

SAEs that are unanticipated, serious, and possibly related to the study intervention will be reported to the IM and NCCIH in accordance with requirements.

- Unexpected fatal or life-threatening AEs related to the intervention will be reported to the NCCIH Program Officer within 7 days. Other serious and unexpected AEs related to the intervention will be reported to the NCCIH Program Official within 15 days.

- Anticipated or unrelated SAEs will be handled in a less urgent manner but will be reported to the IM and NCCIH in accordance with their requirements.

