5. STUDY INTERVENTIONS

5.1 Interventions, Administration, and Duration

The intervention in this study is Mindful Awareness in Body-oriented Therapy (MABT), administered one-on-one by therapists trained in the MABT protocol at the outpatient treatment site where the participant was recruited from and receives their MAT care. Individuals in the MABT intervention group will receive 8 weekly 1.25 hour one-on-one sessions of MABT between baseline and the 3 month follow-up assessment. There are no restrictions to supportive care, medications, or other treatments which intervention group participants may use during their participation in the study with the exception of additional manual (e.g., massage) and/or mind-body therapies of meditation and yoga during the first three months of study engagement (this information is part of the screening process for enrollment, and will be reiterated by the research coordinator at the time of study enrollment). There are no anticipated adverse effects of the intervention other than the possibility of short-term emotional discomfort.

At six months, those in the MABT treatment group with continued substance use will be offered an additional six sessions of MABT between the 6 month and 9 month assessments.

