7. SAFETY ASSESSMENTS

7.1 Specification of Safety Parameters

It is possible that participants may experience anxiety related to questions asked on the questionnaires. For participants who receive MABT, there may be anxiety due to the use of touch in the MABT sessions or the development of a new therapeutic relationship. During the course of the study, interventionists may develop concerns regarding a participant's risk of suicide or harm to self or others, or health concerns such as increased medical symptoms such as pain, or mental health symptoms of severe depression, anxiety, PTSD. Upon entering the study, all participants will be asked to sign a Treatment Information Release Form, which will allow for two-way communication between research and clinical staff to discuss concerns such as those described.

Any medical emergencies, disclosed suicidal ideation, or other urgent concerns for participant safety experienced by the research coordinators or interventionists will be addressed according to the procedures at the clinical site where the participant is seen. Review of these protocols and accessing emergency contact information will be included in the staff training for all study staff. The study staff with the experience will report the event and resolution/follow-up to the principal investigator(s) that day.

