7.3 Adverse Events and Serious Adverse Events

For this study, the following standard AE definitions are used:

Adverse event: An adverse event (AE) is any untoward medical occurrence in a subject during participation in the clinical study or with use of the experimental agent being studied. An adverse finding can include a sign, symptom, abnormal assessment (laboratory test value, vital signs, electrocardiogram finding, etc.), or any combination of these

Serious Adverse Event: A serious adverse event (SAE) is any AE that results in one or more of the following outcomes:

- Death
- A life-threatening event
- Inpatient hospitalization or prolongation of existing hospitalization
- A persistent or significant disability/incapacity
- A congenital anomaly or birth defect
- An important medical event based upon appropriate medical judgment

AEs are graded according to the following scale:

Mild: An experience that does not have a major impact on the patient (e.g., is transient, requires no special treatment or intervention, does not generally interfere with usual daily activities). This includes transient laboratory test alterations.

Moderate: An experience that causes the patient some minor inconvenience, but is alleviated with simple therapeutic treatments. The experience impacts usual daily activities. Includes laboratory test alterations indicating injury, but without long-term risk.

Severe: An experience that causes a substantial disruption to the patient's well-being (e.g., requires therapeutic intervention). The experience interrupts usual daily activities. If hospitalization (or prolongation of hospitalization) is required for treatment it becomes an SAE.

The study will use a form specifically for collection of AEs. AEs will be solicited at all participant followup assessment visits with the RC and collected at all intervention visits by the Interventionists. The AE form will have the following attribution scale:

Not related: The AE is clearly not related to the study procedures (i.e., another cause of the event is most plausible and/or a clinically plausible temporal sequence is inconsistent with the onset of the event).

Possibly related: An event that follows a reasonable temporal sequence from the initiation of study procedures, but that could readily have been produced by a number of other factors.

Related: The AE is clearly related to the study procedures.

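### Section 7.4 exempts minor events from the AE Log before relatedness is judged, so low-severity events possibly related to MABT may go unlogged and unattributed

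*Combined protocol and SAP*

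**What the plan says.** Section 7.4 describes a sequence. When an adverse event (AE) is reported, the Research Coordinator or the MABT interventionist completes a participant event form (PEF), and PEFs go to the project manager each week. The AE Log then takes "all adverse events, with the exception of clinically insignificant events and minor common illnesses and injuries". Four examples follow: cold or flu, scrapes, upset stomach and low-grade headache. Logged events go to the contact PI every two weeks, "who provides the grading and attribution evaluation". The core team discusses AEs monthly, and summaries go to the Independent Monitor quarterly and to NCCIH annually. "Reports will provide information on cumulative incidents", and if these point to greater risk, the investigators and the Monitor consider whether the consent form needs changing. In the annual summary, "the Independent Monitor Report will state that he has reviewed all AE reports".

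Section 7.3 defines an AE with no minimum severity. It has three severity grades. The lowest, Mild, is illustrated by an event that "is transient, requires no special treatment or intervention, does not generally interfere with usual daily activities". It adds: "The AE form will have the following attribution scale". The categories are Not related, Possibly related and Related.

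On the expected effects of MABT, Section 5.1 states: "There are no anticipated adverse effects of the intervention other than the possibility of short-term emotional discomfort". Section 7.1 adds that "there may be anxiety due to the use of touch in the MABT sessions or the development of a new therapeutic relationship".

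Section 9.4 provides that if AEs are found to be related to participation, the MPIs and the Monitor consult the IRB and the NCCIH program officer about continuing risk. It sets no severity threshold for this.

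**The concern.** A filter on trivial events is reasonable in a minimal-risk trial, provided that it removes noise and not signal. Here the criterion is clinical significance, which the plan does not define. Relatedness, the property that matters most for judging an intervention, plays no part in the logging decision. The one adverse effect that Section 5.1 anticipates is short-lived emotional discomfort, which is the kind of event that staff might regard as insignificant.

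At stake is the count of low-severity reactions to MABT that carry a formal attribution. That count informs the consent review in Section 7.4 and the consultation in Section 9.4. Attribution has added weight because Section 7.6 has the annual report tables show aggregate data, not data by arm. In those tables the attribution category is the main stated way to connect an event with MABT.

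**Working it through.** No rate or power figure is involved, so the check sets the provisions side by side.

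1. **Order of steps (7.4).** PEF completed, PEF to project manager, exception applied, event logged, event reported to contact PI, event graded and attributed. The exception comes before the contact PI's attribution. The text does not say who applies it.

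2. **Condition on relatedness.** The exception has none. Section 7.3 puts an attribution scale on the AE form, but the plan does not say that this form is the PEF or who completes the scale at that stage. Even if relatedness were marked on the PEF, 7.4 does not make logging depend on it.

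3. **Can the exception reach MABT's own effects?** Of the three grades in 7.3, only Mild plausibly overlaps with clinical insignificance. The effects named in 5.1 and 7.1 can be mild and transient. The four examples in 7.4 are all minor physical complaints (0 of 4 emotional or psychological). They attach most naturally to the illnesses and injuries part of the exception, so they do not settle how an emotional reaction is handled.

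4. **Is there a route back in?**
   - Unanticipated problems (7.3) must be unexpected, related or probably related, and suggestive of greater risk, all three together. A single mild, anticipated reaction does not qualify. Unexpected frequency counts towards the first criterion, but an excess can be recognised only if the events are counted.
   - The SAE route (7.4) does not apply to minor events.
   - The consultation in 9.4 has no severity threshold but is triggered by a determination of relatedness. An event filtered out earlier has no described path to that determination.

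5. **Do unlogged events reach the summaries?** Section 7.4 does not say whether these are compiled from the log or from PEFs. The Data Monitoring table in 10.3.5 appears to have AEs and rates reviewed weekly by the project manager and MPIs, without naming a source. The Monitor's review of all AE reports is not said to include unlogged PEFs.

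6. **AE collection points by arm (6.1, 6.2.4).** Both arms have 4 follow-up assessments (weeks 12, 24, 39 and 52). MABT adds 8 initial sessions and, for those who take the additional course, up to 6 more: 4 + 8 = 12, or 4 + 8 + 6 = 18, against 4 under usual treatment alone. This bears on how AE counts should be read after any change.

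The number of events affected cannot be derived. The documents give neither a rate of mild related events nor a rate at which the exception would be used.

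**The case against.** The best defence is that an undefined term is not an omission rule. The plan provides a Mild grade and describes the contact PI's grading for logged events. If Mild events were excluded as a class, that grade would be nearly empty, so Mild and clinically insignificant cannot be the same thing. Emotional discomfort and touch-related anxiety are named in advance, which gives staff reason to take such a report seriously. This stands, and it rules out the stronger reading that a reader might infer: that mild MABT-related events are kept off the log as a matter of course.

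A reader might also infer that these events never reach the Independent Monitor or NCCIH. The documents do not support that, because the source of the summaries is unstated and the weekly review in 10.3.5 may draw on PEFs.

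Other safeguards count too. PEFs preserve the source record, and source documents and AE logs are audited quarterly (10.3.5). Sessions are audio-recorded and process evaluations reviewed in supervision (10.3.1). Urgent safety concerns go to the principal investigators the same day (7.1). Depression, anxiety and PTSD scales are collected in both arms. It would therefore be too strong to call the logged mild events the main tolerability information on MABT. Some in-session discomfort is also part of the therapy (2.2) and may not be an AE at all.

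These safeguards narrow the problem without closing it. An audit checks compliance, and a team can comply with 7.4 while leaving a related event off the log. Supervision is not AE counting. The first symptom assessment after baseline is at week 12, whereas the initial sessions run from weeks 1 to 11, so a brief reaction to an early session may not show in the scales. None of these routes supplies formal attribution.

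**Conclusion.** The point holds as a permission in the wording, not as a demonstrated loss. Low-severity events possibly related to MABT can be left unlogged and without the contact PI's attribution, and so may miss the cumulative counts and the 9.4 consultation. Any effect on the reports to the Monitor and NCCIH remains open.

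The size is unquantified but small. It concerns at most part of one of three severity grades, in a trial that Section 7.6 describes as minimal risk. Mild anticipated events alone are unlikely to change the consent form. SAE reporting and the efficacy analyses are untouched. The conclusion assumes that the steps in 7.4 are carried out in the order written and that no separate operating procedure already ties logging to relatedness. Severity is low; this is a cheap improvement.

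**What to change.** Amend 7.4 in one or two sentences:

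- Limit the exception to minor events judged Not related on the 7.3 scale.
- For any event proposed for exclusion, have the contact PI make or confirm the relatedness call from the PEF. It should not rest with the interventionist alone, who would otherwise decide whether a reaction to their own session escapes the log.
- Log, grade and attribute every Possibly related or Related event, whatever its severity, including session-related distress reported as an AE.

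This keeps 1 of the 3 attribution categories within the exception and takes 2 out. Unrelated colds and scrapes stay off the log. PEFs are already completed and submitted weekly, so no new form is needed.

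The cost is a short extra check by the contact PI and a few more Mild entries. Most of these will fall in the MABT arm, partly because its sessions add AE collection points. Any report of AE counts by arm should say so, to avoid reading closer observation as greater harm.

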7.5 Follow-up for Adverse Events

During the study, participants will be attending an outpatient treatment program for OUD where they can be monitored and have access to clinical staff. Thus, AEs will be managed in conjunction with OUD treatment program staff, with permission from the participant. If a participant is no longer involved in opioid use disorder treatment, AEs will be managed by the research staff; however, if danger to self or others is identified, crisis intervention procedures will be initiated that may include referral or contacting community mental health emergency services.

7.6 Safety Monitoring

Given the IRB-determined minimal risk and early Phase II nature of the research, there will be no Data Safety Monitoring Board or Independent Monitoring Committee. Independent safety and data oversight will be provided by the Independent Monitor (IM) [name] M.D., an independent physician and appropriate expert with relevant expertise for advising the study investigators. He is qualified to review the patient safety data generated by this study because of his unique expertise in the area of opioid use disorder treatment as the Medical Director of the Addiction Recovery Service in a local medical system, Swedish Medical Center.

The IM will meet with the study team at the start of each study year to get an overview of the study, study implementation expectations, and study progress; and will receive quarterly brief reports detailing subject accrual, enrolled subject status and adherence, and AE/SAE summaries, and more frequent reporting by request if concerns arise. A DSM annual summary report will be provided to the IM in conjunction with required annual reporting to the IRB and NCCIH, which will detail monthly recruitment, enrollment, and retention against milestones; participant adherence, AE/SAE summary, and any other safety-related study information (e.g., serious non-compliance). Annual report tables will be generated only from aggregate (not by group assignment) baseline and aggregate safety data for the study population.

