3. STUDY DESIGN

Design Overview: A two-group (n = 165/165), randomized, repeated measures design will be employed. Three hundred thirty individuals with OUD engaged in medication treatment will be recruited at one of five outpatient treatment sites: Harborview Medical Center, Country Doctor Community Health Centers, North Olympic Healthcare Network, Cascade Medical Advantage, and Evergreen Treatment Services. Enrolled patients will be individually randomized within sites to receive MABT+TAU (experimental group), or TAU alone (control). Assessments will be administered at baseline, post-intervention (3 months from baseline), and at 6, 9 and 12 months follow-up. An additional six sessions of MABT will be offered to those randomized to MABT who have continued substance use at six months.

Randomization: Following baseline data collection, participants will be randomized to treatment group by the Research Coordinator. [name], the project statistician, provided a randomization program programmed in Microsoft BASIC. Randomization will be specific to each study site and stratified by sex (approximately equal numbers of men and women assigned to each study group at each site) and baseline self-reported chronic pain. The algorithm used for randomization is a modification of a minimization method [96] based on an overall imbalance score which measures how far out of balance (within strata) the study is for a given set of random assignments. Participants will be informed of their assignment within one week of the initial appointment. Prior MABT studies showed no loss due to randomization to treatment group, thus we do not expect randomization to precipitate significant attrition. The Research Coordinator at each facility will not be blind to condition and will inform participants of their treatment condition and MABT therapist.

Measures: The outcome measures are described below (see also Table 1 in Précis).

Primary Objectives: The primary outcome is patient-reported days of illicit opioid use. Self-reported substance use is the recommended approach for intervention studies.[97] Days of illicit opioid use is defined as the number of reported days of use in last 90 days (baseline assessment) or since and including the last assessment date (follow-up assessments) in which opioids other than MAT (buprenorphine or methadone) are reported.

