9.4 Interim Analyses and Stopping Rules

No interim efficacy or futility analyses are planned because of the minimal risk level of the study and because patient outcomes are very unlikely to be worse in the intervention group in the study.

This study will be stopped prior to its completion only after discussion with and input from NCCIH if: (1) the intervention is associated with severe adverse effects that call into question the safety of the intervention; (2) difficulty in study recruitment or retention will significantly

impact the ability to evaluate the study endpoints; (3) any new information becomes available during the trial that necessitates stopping the trial; or (4) other situations occur that might warrant stopping the trial.

Pertaining to the likelihood of adverse events, prior studies employing MABT to individuals with mental health concerns including two NIH-funded studies for individuals with substance use disorder, many of whom had moderate-severe depression and/or anxiety symptoms, and three additional studies for women with sexual trauma, have not identified significant risks associated with this intervention. However, should adverse events occur that are determined to be related to study participation, the MPIs and independent monitor (IM) will consult with both the UW IRB and the NICCH Program Officer about the likelihood of continued risk to study participants and will make a decision about whether it is necessary to stop the trial.

Should accrual monitoring demonstrate the need, the MPIs will consult with the data analyst and the IM to assess the impact of significant data loss due to problems in recruitment, retention, or data collection. Factors external to the study when interpreting the data, such as scientific developments or the new availability of proven clinical services that could have an impact on the safety of the participants, the performance of the study or the ethics of the study, will be reviewed by the MPIs annually.

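### The Independent Monitor's annual safety tables are pooled over arms and no by-arm safety table is planned, so they cannot show whether severe events are associated with MABT

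*Combined protocol and SAP*

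**What the plan says.** Section 3 sets the allocation: "A two-group (n = 165/165), randomized, repeated measures design will be employed".

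On oversight, section 7.6 says that "there will be no Data Safety Monitoring Board or Independent Monitoring Committee" and appoints a single Independent Monitor. The monitor "will receive quarterly brief reports detailing subject accrual, enrolled subject status and adherence, and AE/SAE summaries", may ask for more frequent reports if concerns arise, and receives an annual summary. For that summary the format is explicit: "Annual report tables will be generated only from aggregate (not by group assignment) baseline and aggregate safety data". The format of the quarterly reports is not stated. The monitoring table in 10.3.5 lists AEs and rates without saying whether they are split by arm.

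Section 9.4 plans no interim efficacy or futility analysis. It gives as one reason for stopping that "the intervention is associated with severe adverse effects that call into question the safety of the intervention". It sets no threshold and names no table or analysis on which this would be judged. It adds that events judged related to participation lead the MPIs and the monitor to consult the IRB and the NCCIH Program Officer.

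Under 7.4, logged AEs "will be reported every 2 weeks to the contact PI, who provides the grading and attribution evaluation". Under 7.3, attribution is to study procedures, and AEs are solicited at follow-up visits in both arms and also "collected at all intervention visits by the Interventionists".

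**The concern.** Whether an intervention is associated with severe events is, in a randomized trial, most directly answered by comparing the arms. The one scheduled safety report whose format is fixed hides the arm from the only independent reviewer.

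This matters because case-level attribution is hard in this population. Table 3 of section 4 describes expected participants as 67% with moderate to severe depression, 56% with moderate to severe PTSD and 31% injecting drugs. Section 7.1 names suicide risk, increased pain and worsening mental health as possible concerns. Such events can plausibly arise in either arm, and each taken singly can be put down to the underlying condition. An excess in one arm would then show only when the arms are set side by side. What is at stake is the chance of noticing an imbalance during the trial.

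**Working it through.** The plan gives no figure to reproduce here. The check is a reading of the safety sections plus a small illustration.

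**1. Is there a by-arm safety table anywhere?**
- 7.2: its title mentions analysing safety parameters, but the text gives no analysis.
- 7.4: quarterly AE summaries to the monitor; no statement about arm.
- 7.6: quarterly reports, format unstated; annual tables pooled.
- 9.6: analyses of efficacy, retention and dose; none of adverse events.
- 10.3.5: AEs and rates; no statement about arm.

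So the annual tables are pooled by rule, and no other section promises a split.

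**2. What can a pooled count show?** The documents give no event rate, so the counts below are assumptions. With 165 per arm and a fixed total of 10 events, under no arm difference each event falls in either arm with probability 1/2. The two-sided exact binomial p is twice the upper tail.
- Pooled line for any split: 10/330 = 3.0%.
- 5 v 5: 5/165 = 3.0% in each arm; p = 1.00.
- 8 v 2: 4.8% v 1.2%; p = 2 × (45 + 10 + 1)/1024 = 112/1024 = .109.
- 9 v 1: 5.5% v 0.6%; p = 2 × (10 + 1)/1024 = 22/1024 = .021.

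Fisher's exact test on the 165/165 table gives nearly the same: .104 for 8 v 2 and .020 for 9 v 1.

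For other assumed totals (Fisher):
- 6 events (6/330 = 1.8%): 3 v 3, p = 1.00; 6 v 0, p = .030.
- 20 events (20/330 = 6.1%): 10 v 10, p = 1.00; 16 v 4 (9.7% v 2.4%), p = .009.

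One pooled line fits both no difference and a large one. At small totals, however, even a by-arm table separates statistically only a lopsided split.

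**3. Would crude counts by arm be comparable?** Planned contacts at which AEs are collected:
- TAU: 4 follow-up visits (weeks 12, 24, 39, 52).
- MABT: 4 + 8 sessions = 12, or 4 + 8 + 6 = 18 with the additional sessions.

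The ratio is 12/4 = 3.0 to 18/4 = 4.5. A raw by-arm count could therefore suggest harm through closer observation alone, so the source of each report has to be shown.

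**The case against.** The strongest reply is that the monitor does not depend on the annual tables. Section 7.4 sends the monitor SAEs that are unanticipated and possibly related, and also those that are anticipated or unrelated. It requires a statement that all AE reports were reviewed. Section 7.6 adds quarterly summaries, not said to be pooled, and reports on request. Section 9.4 describes the safety decision as working through events judged related to participation, not through an arm comparison, and nothing ties the first criterion to the annual tables.

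Most of this stands. A reader might infer that the safety rule does not work as written, or that the contact PI's attribution is the only remaining signal. The documents support neither: the relatedness route can operate, and the monitor sees individual reports. Nor may the pooling rule be extended to the quarterly reports, whose format is open.

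What the reply does not supply is a comparison. Grading and attribution are made by the contact PI, who is not independent of the study, and refer to study procedures as a whole. Reports on request need a prior concern, and pooled tables cannot raise one about imbalance.

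Two further points are fair. The event counts are hypothetical: 7.2 expects few or no study-related events and says that prior MABT studies had no serious ones. Also, the documents give no rate for overdose, admission or suicidality, so the weakness of case-level attribution is a reasoned expectation, not a documented figure.

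**Conclusion.** The point holds in a limited form. The annual tables, pooled by rule, cannot show whether severe events are associated with MABT, and no section provides a by-arm table that could. The case-level routes are real but do not replace a comparison.

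The size cannot be given as a rate. With an assumed 10 events, 3.0% pooled hides anything from 5 v 5 to 9 v 1 (p = .021), while 8 v 2 (p = .109) would remain inconclusive even if shown by arm. The benefit is that an imbalance becomes visible to the monitor, not that a test gains much power.

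Priority is modest. The study was judged minimal risk, which is a reasonable ground for having no DSMB. It is a weaker ground for withholding the arm from the one independent reviewer, who has no role in outcome assessment.

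**What to change.** In 7.6, replace the pooled-only rule, for the monitor alone, with a closed table in both the annual and the quarterly reports:
- AEs by grade, and SAEs, by coded arm (A/B, decodable on the monitor's request). Show severe grade and SAE separately, because 7.3 defines them separately and 9.4 refers to severe effects.
- Denominators: participants randomized in each arm and participants assessed at each follow-up visit.
- Events solicited at the four common follow-up visits in one block, and events reported only at MABT sessions in another.

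State in 9.4 that the monitor considers this table, alongside the case reports, when the first stopping criterion is discussed. No numerical threshold is proposed here. The investigators and the statistician, who is to be blind under 6.2.3, keep the pooled tables.

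The cost is one added table per report from data already collected, plus a safeguard. Whoever prepares it must keep it from the study team. The data manager is a natural choice, but under 10.2 maintains the databases together with the project manager and MPIs, so the separation must be written down. The A/B code may be guessable from the block of session-reported events. This is tolerable for a monitor who may ask for the code anyway, but it is a further reason to restrict circulation.
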